## **1.2 BACKGROUND ON RO7020531**

RO7020531, an oral double prodrug of the TLR7-specific agonist, RO7011785, is being developed for the treatment of CHB patients. A prodrug approach was chosen for oral delivery of the TLR7 agonist RO7011785 in order to improve bioavailability and limit TLR7 activation in the gastrointestinal (GI) tract, which may be associated with GI intolerability. Non-clinical studies with RO7020531 suggest that it is rapidly converted to the active metabolite RO7011785. Data from in vivo studies with RO7020531 and in vitro studies with RO7011785 support immune activation as the mechanism of action.

See the [RO7020531 Investigator Brochure](#) (IB) for details on non-clinical studies.

### **1.2.1 Previous Non-Clinical Studies**

#### **1.2.1.1 Non-Clinical Pharmacology**

RO7011785 showed in vitro potency to activate TLR7 and triggered downstream TLR7-mediated nuclear factor-kappa B (NF- $\kappa$ B) signaling in an engineered HEK293 reporter cell line expressing human TLR7. RO7011785 was shown to be a selective hTLR7 agonist with less potency to activate hTLR8 in vitro. Ex vivo stimulation of human peripheral blood mononuclear cells (PBMCs) from healthy donors by RO7011785 resulted in dose-dependent induction of various cytokines and chemokines, including IFN- $\alpha$ , tumor necrosis factor- $\alpha$  (TNF- $\alpha$ ), interleukin-6 (IL-6), and IFN gamma-inducible protein 10 (IP-10).

#### **1.2.1.2 HBV Animal Model**

The anti-HBV activity of RO7020531 was evaluated in an HBV mouse model. In this model, C57BL/6 mice were injected with recombinant adeno-associated virus (AAV) harboring 1.3 copies of the HBV genome, and demonstrated high levels of HBV viral makers including HBV DNA, HBsAg, and HBeAg. Oral administration of RO7020531, QW or QOD for 6 weeks, proved to have in vivo anti-HBV activity in this mouse model, i.e., clear reduction in HBV DNA and HBsAg (by more than 1 log after the 42-day treatment period). With the same administration frequency, higher doses resulted in faster and greater reduction in HBV DNA and HBsAg. With the same dose of 100 mg/kg, QOD administration resulted in greater viral reduction on Day 42 than QW administration. In addition, RO7020531 induced interferon-stimulated gene (ISG) expression in peripheral whole blood in this mouse model.

#### **1.2.1.3 Non-Clinical Pharmacokinetics and Metabolism**

RO7020531 showed high oral bioavailability and rapid conversion to the active moiety, RO7011785. RO7011785 exhibited a relatively short half-life ( $t_{1/2}$ ) of 1.51 hours in rats and 2.12 hours in monkeys, moderate systemic clearance (CL) of ~50% liver blood flow in rats, and CL of ~30% liver blood flow in monkeys. RO7011785 had a moderate volume of distribution ( $V_{ss}$ ) in the range of body water or slightly higher for both rats and

monkeys. Differences in metabolite exposure were noted between species, although RO7011785 was the predominant metabolite in both rats and monkeys, confirming good conversion to active drug.

Conversion of RO7020531 to the active form RO7011785 was observed in animal and human hepatocytes, with both the ester hydrolysis and aldehyde oxidase-mediated pathways active. The relative strength of the oxidase versus esterase pathways varied between species and influenced the concentrations of the different intermediate prodrugs: RO7033805 was the predominant intermediate for cynomolgus monkey, whereas RO7018822 was the predominant intermediate for mouse, rat, and human.

RO7020531 was found to be a good substrate of multidrug resistance protein 1 (MDR1; P-glycoprotein [P-gp]), with a high apparent membrane permeability. Therefore, in vivo drug-drug interactions (DDI) due to co-administration with MDR1 inhibitors cannot be excluded. However, interactions of strong MDR1 inhibitors with the absorption of RO7020531 are considered unlikely due to the high permeability, high solubility, and high oral bioavailability of RO7020531, which makes it unlikely that MDR1 plays a major role in RO7020531 transintestinal absorption in vivo.

RO7011785 can be directly glucuronidated by UDP-glucuronosyltransferase 1A1 (UGT1A1); thus, drug-drug interactions with UGT1A1 inhibitors cannot be excluded. Drug-drug interaction potential was low, as determined in vitro with cytochrome P450 (CYP) enzymes and with transporters (organic anion transporting polypeptide 1B1 [OATP1B1], OATP1B3, organic anion transporter 1 [OAT1], OAT3, and breast cancer resistance protein [BCRP]). Therefore, the interactions with CYPs and substrates for hepatic uptake transporters and kidney transporters (for example NUCs) in vivo are unlikely.

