### **Special Concomitant Medications in Chronic Hepatitis B Patients (Part 2)**

The following medications are not prohibited in Part 2 of the study. However, caution is required in case of co-administration with the study drug, and the Sponsor should be informed before these drugs are administered.

- 
- Drugs that reduce renal function or compete for active tubular secretion may increase serum concentrations of either study drug or the co-administered drug.
  - Drugs metabolized by aldehyde oxidase including famciclovir and/or inhibiting this enzyme including tamoxifen, raloxifen, cimetidine, promethazine, clozapine and chlorpromazine, which could decrease the formation of RO7011785.

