### 1.3.2 Benefit-Risk Assessment

No prior clinical experience with RO7020531 exists. The evaluation of potential risks of treatment and specific tests, observations, and precautions required for clinical studies with RO7020531 are based on information from non-clinical toxicology and safety pharmacology studies, and on information from clinical studies with other TLR7 agonists. Safety and tolerability will be carefully assessed, and HVs/patients will be closely monitored. The [RO7020531 IB](#) (Guidance to the Investigator) summarizes potential risks and key risk management activities to consider when dosing this compound.

[REDACTED]

In two Phase I studies with RO7020531, 19 subjects (dosed with 140 mg or higher) developed flu-like symptoms with initial onsets usually after the first, second, or the third dose. *In addition, in Study NP39305 Part 2 Cohort 4, one patient experienced an SAE of flu-like syndrome (see Section 1.2.2).* The flu-like symptoms were mild in the majority of these subjects, [REDACTED]

[REDACTED]

As for all early clinical studies in HVs, there is no direct benefit to the subjects participating in Part 1 of the study. However, this study will be essential in the development of a new treatment for chronic HBV infection, and for selecting the most appropriate dose for a study in HBV-infected patients. It is possible that no long-term benefit to CHB patients may occur in Part 2 of this study; however, data generated in these patients will enable further development of RO7020531 as potentially part of a clinical cure for CHB.

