#### **4.2.3.2 Part 2: Chronic Hepatitis B Patients**

Patients who meet any of the following criteria will be excluded from study entry:

1. Pregnant (positive pregnancy test) or lactating women.
2. History of liver cirrhosis.
3. History or other evidence of bleeding from esophageal varices.

4. Decompensated liver disease (e.g., Child-Pugh Class B or C clinical classification or clinical evidence such as ascites or varices).
5. History or other evidence of a medical condition associated with chronic liver disease other than HBV infection (e.g., hemochromatosis, autoimmune hepatitis, alcoholic liver disease, toxin exposure, thalassemia, nonalcoholic steato-hepatitis, etc.). A clinical diagnosis of fatty liver is allowed provided that non-alcoholic steatohepatitis (NASH) has been excluded by liver biopsy.
6. Documented history or other evidence of metabolic liver disease within one year of randomization.
7. Positive test for Hepatitis A virus (IgM anti-HAV), Hepatitis C virus (HCV), Hepatitis D virus, Hepatitis E virus (HEV), or human immunodeficiency virus (HIV).
8. Expected to need systemic antiviral therapy other than that provided by the study at any time during their participation in the study, with the exception of oral therapy for Herpes simplex virus type I (HSV I) or HSV II.
9. History of or suspicion of hepatocellular carcinoma or alpha fetoprotein  $\geq 13$  ng/mL at screening.
10. History of immunologically mediated disease (e.g., inflammatory bowel disease, idiopathic thrombocytopenic purpura, lupus erythematosus, autoimmune hemolytic anemia, scleroderma, severe psoriasis, rheumatoid arthritis, multiple sclerosis, or any other autoimmune disease).
11. History of clinically significant cardiovascular (including postural hypotension), endocrine, renal, ocular, pulmonary or neurological disease (as per Investigator's judgment).
12. History of clinically significant GI disease including inflammatory bowel disease, peptic ulcer disease, GI hemorrhage, or history of pancreatitis.
13. History of clinically significant psychiatric disease, especially major depression (significant psychiatric disease is defined as treatment with an antidepressant medication or a major tranquilizer at therapeutic doses for major depression or psychosis, respectively, or any history of the following: a suicide attempt, hospitalization for psychiatric disease, or a period of disability due to a psychiatric disease).

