### **4.5 CONCOMITANT THERAPY**

#### **4.5.1 Permitted Therapy**

##### **4.5.1.1 Part 1: SAD and MAD in Healthy Volunteers**

As a general rule, no concomitant medication (including health supplements, vitamins or herbal remedies) will be permitted, unless the rationale for use is discussed between the Investigator and Sponsor and is clearly documented. The following medications are exceptions:

- Medications used to treat AEs may only be prescribed after consultation with the Sponsor (with the exception of acetaminophen/paracetamol), unless there is a medical need to ensure the well-being of the subject that should not be delayed. All therapy and/or medication administered to manage AEs should be recorded on the AE eCRF.
- Hormone replacement therapy (HRT), continue using if initiated two months prior to study start.
- Acetaminophen/paracetamol is allowed up to a maximum dose of 2 g per day. During the period of confinement to the clinical research unit, subjects will be restricted from the use of acetaminophen/paracetamol and other non-prescription medications beginning 4 hours prior to dosing through 4 hours after dosing unless deemed necessary to treat an AE by the Investigator.

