##### **4.5.2.2 Part 2: Chronic Hepatitis B Patients**

Prohibited medications include:

- Any systemic anti-neoplastic (including radiation) or immune-modulatory treatment (including systemic oral or inhaled corticosteroids IFN or PEG-IFN) at any time within the 8 weeks prior to the first dose of study drug and until the end of follow-up period. Eye drop-containing and infrequent inhaled corticosteroids are permissible up to 4 weeks prior to the first dose of study drug.
- Any systemic antiviral therapy other than nucleos(t)ide analogues (Cohorts 1, 2 and 3 only) at any time from 30 days before screening until the end of follow-up period, with the exception of oral therapy for HSV I or HSV II. Investigational drugs or herbal and other remedies which are being taken by the patient for possible or perceived effects against HBV are prohibited.

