### **4.5.3 Special Concomitant Medications in Chronic Hepatitis B Patients (Part 2)**

The following medications are not prohibited in Part 2 of the study. However, caution is required in case of co-administration with the study drug, and the Sponsor should be informed before these drugs are administered.

- Drugs that reduce renal function or compete for active tubular secretion may increase serum concentrations of either study drug or the co-administered drug.
- Drugs metabolized by aldehyde oxidase including famciclovir and/or inhibiting this enzyme including tamoxifen, raloxifen, cimetidine, promethazine, clozapine and chlorpromazine, which could decrease the formation of RO7011785.

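### The Part 2 caution-and-notification list does not name UGT1A1 inhibitors, although Section 1.2.1.3 leaves that interaction with the active metabolite open

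*Combined protocol and SAP*

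**What the plan says.** Section 1.2.1.3 goes through the interaction routes in turn. For UGT1A1, which acts directly on the active metabolite RO7011785, it ends with: "thus, drug-drug interactions with UGT1A1 inhibitors cannot be excluded". For MDR1 it raises the possibility in similar terms, but then argues that an effect on absorption is improbable. It also judges CYP and transporter interactions unlikely from in vitro work. No such argument follows for UGT1A1.

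Section 4.5.3 covers drugs that Part 2 patients may take but only with care, and for which "the Sponsor should be informed before these drugs are administered". It has two entries. The first reads in part: "Drugs that reduce renal function or compete for active tubular secretion may increase serum concentrations". The second covers substrates and inhibitors of aldehyde oxidase, "which could decrease the formation of RO7011785". The synopsis carries the same two entries.

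Neither version mentions UGT1A1, and nor do the prohibited therapies (Section 4.5.2.2) or the dietary rules (Section 4.5.4). For a drug on no list, Section 4.5.1.2 asks that it be reported to the Investigator and recorded on the eCRF.

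Part 1 works differently. There, "As a general rule, no concomitant medication (including health supplements, vitamins or herbal remedies) will be permitted" unless the reason is discussed with the Sponsor, apart from a few stated exceptions.

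**The concern.** Section 4.5.3 is where the interaction findings become an instruction to sites. It takes entries that are only possible, as its own wording (may, could) shows. An interaction that the non-clinical section declines to rule out meets that standard, yet it is missing.

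Direction matters too. The listed aldehyde oxidase inhibitors could lower the amount of active drug formed. Blocking glucuronidation of RO7011785 would be expected to raise exposure to it, which is the direction that matters for safety: Section 5.2.1 describes flu-like symptoms with this drug class as dose-dependent. At stake is a site starting a UGT1A1 inhibitor in a Part 2 patient with no prompt for caution and no word to the Sponsor beforehand.

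**Working it through.** The plan gives no figure for this interaction, so the main check is a comparison of text.

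**1. Routes side by side**

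| Route | Section 1.2.1.3 | Section 4.5.3 and synopsis |
|---|---|---|
| Aldehyde oxidase | active in converting the prodrug | listed |
| Kidney transporters / tubular secretion | interaction judged unlikely | listed |
| MDR1 | raised, then discounted | not listed |
| CYP enzymes, hepatic uptake transporters | interaction judged unlikely | not listed |
| UGT1A1 | left open, not discounted | not listed |

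UGT1A1 is the only route that is both left open and unlisted. The tubular-secretion row shows how low the threshold for listing is.

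**2. Size of the effect**

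If a fraction f of RO7011785 clearance ran through UGT1A1 and were fully blocked, with linear kinetics and unchanged formation, AUC would rise by a factor of 1/(1 − f). The documents give no f. Purely as assumptions:
- f = 10% gives 1/0.90 = 1.11
- f = 25% gives 1/0.75 = 1.33
- f = 50% gives 1/0.50 = 2.0

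Nothing in the documents favours one of these. Section 3.2.3.1 expects extensive renal elimination, by analogy with a related compound, which points towards a small f. The effect cannot be sized.

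**3. Exposure context only**

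Section 1.2.2 gives a mean Day 1 AUC in patients of 2814 ng*hr/mL and a monkey LOAEL exposure of 2780. The ratio is 2814/2780 = 1.012. The section discusses 150 mg and 170 mg together and does not say how the mean was formed. The ratio describes current exposure and says nothing about the size of an interaction.

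**4. What already operates in Part 2**

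- Before the first dose: co-medication is collected from 4 weeks before screening (Sections 4.5.1.2 and 4.6.1.1), and the Cohort 4 schedule collects it again on Day -1.
- After dosing: PK is sampled in Cohort 4 on Days 1, 3, 5, 7, 21 and 41 (Appendix 1, with 24-hour samples after Days 1 and 41). Safety and PK are reviewed patient by patient (Section 4.6.2.2), and intolerable, unmanageable flu-like symptoms lead to discontinuation (Section 4.7.1.1).
- Not covered: prior Sponsor notice for an unlisted drug. A drug started after the Day 21 visit would meet no scheduled PK sample until the Day 41 visit.

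**5. Reach**

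Section 1.2.2 counts 30 patients dosed in Cohorts 1 to 3 and 9 in Cohort 4 by 01 May 2020. Cohort 4 takes up to 15, so without replacements at most 15 − 9 = 6 remain.
- Filled to 15 (12 active, 3 placebo): the first 9 include 6 to 9 active patients, leaving 12 − 9 = 3 to 12 − 6 = 6 active.
- Stopped at 10 (8 active, 2 placebo): 10 − 9 = 1 patient remains, so 0 or 1 active.

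Patients still on treatment on that date would be added; the documents do not give their number.

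**The case against.** The strongest reply is that no rule is broken. Nothing in the protocol says that every interaction not ruled out must appear in Section 4.5.3, and where to set that threshold is for the Sponsor. That stands, so this is an improvement to propose and not an error. It does not explain why kidney-transporter interactions, judged unlikely, earn an entry while one left open does not.

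Second, no harm is shown. The documents name no UGT1A1 inhibitor that a Part 2 patient might take. Any that belongs to a prohibited class (Section 4.5.2.2) is already barred. The half-life of about 4 hours against a 48-hour interval also argues against accumulation: even doubled to 8 hours it leaves 48/8 = 6 half-lives between doses. This too stands, and keeps the point minor. It bears on carry-over between doses, however, and not on the AUC after each dose.

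Third, regular co-medication is known to the Investigator before the first dose. This narrows the gap mainly to drugs started on study, and to the formal steps of caution and Sponsor notice.

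Fourth, guidance may sit elsewhere. Section 1.3.2 says that the Investigator's Brochure "summarizes potential risks and key risk management activities to consider when dosing this compound", and parts of Sections 1.3.2 and 5.2.1 are redacted. None of this can be checked here. The list in Section 4.5.3 is itself shown without redaction.

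**Conclusion.** The omission is confirmed and minor. In the protocol text as supplied, UGT1A1 inhibition alone prompts no caution and no prior Sponsor notice in Part 2. The effect on exposure is unknown and possibly small. The practical reach is at most 6 Cohort 4 patients still to be dosed on 01 May 2020, assuming no replacements, plus any then on treatment. The conclusion assumes that neither the Brochure nor the redacted text already gives the instruction.

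Three stronger readings are not supported:
- A reader might infer from 2814 against 2780 that a UGT1A1 inhibitor would take patients past the exposure limit in Section 3.1.2.2. The documents give no share of clearance through UGT1A1, so no such prediction can be made.
- A reader might infer that these drugs would go unnoticed. Screening, eCRF recording, PK sampling and individual review all remain in place.
- A reader might extend the point to the whole study. In Part 1 co-medication generally needs discussion with the Sponsor, and the 30 patients in Cohorts 1 to 3 had already been dosed.

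**What to change.** Add one entry to the list in Section 4.5.3 and to the matching synopsis list: *UGT1A1 inhibitors, which could increase RO7011785 exposure*. If the Sponsor holds data that discount the interaction, a sentence to that effect in Section 1.2.1.3, as is given for MDR1, would settle the matter instead.

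The cost is one line in two places and a few extra notifications to the Sponsor. Eligibility, assessments and analysis do not change.

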#### **1.2.1.4 Toxicology and Safety Pharmacology**

Repeat-dose toxicity studies with treatment duration of up to 13 weeks have been performed with RO7020531 in rats and monkeys. The effects observed were considered to be consistent with exaggerated pharmacology, i.e., TLR7 agonism leading to the intended immune/cytokine stimulation and subsequent tolerability or proinflammatory findings. QOD and QW dosing regimens were investigated in Good Laboratory Practice (GLP) toxicology studies; QW dosing was better tolerated. The no-observed-adverse-effect-level (NOAEL) for the 13-week rat toxicology study was 3 mg/kg QOD (area under the concentration–time curve for males and females [AUC M/F]=186/503 h•ng/mL) and 30 mg/kg QW (AUC M/F=2950/4660 h•ng/mL). The NOAEL for the 13-week monkey toxicology study was 3 mg/kg QOD (AUC M/F=858/706 h•ng/mL) and 10 mg/kg QW (AUC M/F=3340/2960 h•ng/mL).

Neither the double prodrug RO7020531, nor its metabolites RO7011785 and RO7018822, significantly affected potassium channels in the in vitro human ether-à-go-go-related gene (hERG) assay. Dosing at  $\geq 3$  mg/kg in monkeys caused reversible heart rate increase (with decreased RR interval and shortened QT and/or heart-rate corrected QT [QTc] interval), non-adverse increase in PR interval and increase in body temperature. There were no RO7020531-related effects on respiratory or central nervous system (CNS) function in rats up to the highest dose tested (300 mg/kg).

No genotoxic potential was observed for RO7020531 in the Ames test, nor in the in vitro and in vivo micronucleus test. No evidence of teratogenicity or embryo-fetal toxicity was observed in definitive (GLP) embryo-fetal toxicity studies in rats (up to 150 mg/kg/day, with AUC0-24h of 13500 ng•h/mL) or rabbits (up to 100 mg/kg/day, with AUC0-24h of 46700 ng•h/mL), other than increased incidences of non-adverse fetal skeletal variations. In a definitive (GLP) fertility study in male and female rats, no adverse effects of RO7011785 on mating performance, fertility, or early embryonic development were noted up to the highest tested dose of 300 mg/kg QOD, despite slightly reduced body weight gain in both males and females.

See the [RO7020531 IB](#) for details on the properties of RO7020531 and RO7011785.

### **1.2.2 Previous Clinical Experience**

Study NP39305 is the first-in-human study of RO7020531.

*As of 01 May 2020, 110 healthy volunteers (HVs) in Part 1, and 30 CHB patients from Cohorts 1 to 3 and 9 CHB patients from Cohort 4 from Part 2 have been dosed in Study NP39305. The data from subjects in Part 1 and from patients in Cohort 1 in Part 2 were reviewed by IMC and shared with investigators. The treatment with RO7020531/placebo at all dose levels (Part 1: 3 mg, 10 mg, 20 mg, 40 mg, 60 mg, 100 mg, 140 mg, 170 mg; Part 2: 150 mg) was considered safe and had acceptable tolerability. An event of flu-like syndrome of moderate intensity was reported from a treatment naïve CHB patient from Part 2 Cohort 4 on Day 3. It was assessed as serious as it required or prolonged hospitalization and as related to the study drug by the investigator, and it resolved on Day 5. Adverse events (AEs) potentially related to pharmacodynamic (PD) effects expected with TLR7 agonist treatment were reported at dose levels >100 mg, including three HVs and seven CHB patients. They showed reversible signs and symptoms of immune activation after repeated dosing (e.g. flu-like symptoms) that resolved without sequelae. Apart from transient cytopenia observed in one of the patients, which improved during the dosing period, there have been no clinically significant changes in any other safety parameters, including laboratory assessments, vital signs and ECGs.*

RO7020531 showed a predictable PK profile. Similar to pharmacokinetics in single (SAD) and multiple (MAD) ascending dose cohorts from HVs, the active TLR7 agonist,

RO7011785, appeared rapidly in plasma following 150 and 170 mg dosing of CHB patients on Day 1 with a  $T_{max}$  ranging from 1.0 to 2.0 hr and was eliminated relatively quickly from plasma with a mean terminal half-life of ~4 hours.

Individual  $C_{max}$  and  $AUC_{0-inf}$  of RO7011785 following 150 and 170 mg of RO7020531 in CHB patients appears to be within the range of prediction from SAD/MAD healthy volunteer data. However, the mean RO7011785  $AUC_{0-inf}$  of 2814 ng\*hr/mL on Day 1 is slightly higher (~15%) than the expected value, with greater inter-subject variability, and numerically comparable to mean exposure associated with the monkey lowest observed adverse effect level (LOAEL) (2780 ng\*hr/mL).

*After Study NP39305 had been started, Study YP39553 was initiated. YP39553 was a Phase 1 bridging study to evaluate the PK, PD, and safety/tolerability of RO7020531/placebo in Chinese HV in 4 SAD cohorts (40, 100, 140, and 170 mg) and three MAD cohorts (100 mg, 150 mg and 150 mg). This study has been completed. A total of 70 Chinese HV were dosed in study YP39553. The treatment with RO7020531/placebo was safe with acceptable tolerability when administered orally as a single dose of up to 170 mg and as multiple doses up to 100 mg QOD. A total of nine subjects (8 subjects from the MAD 150 mg cohorts and one subject from the SAD 170 mg cohort) experienced pyrexia/flu-like symptoms after the first, second, or the third dose of the study drug. Of these nine subjects with flu-like symptoms, six had AEs of moderate intensity and three had AEs of mild intensity. In all these subjects, there were no clinically significant changes in vital signs (except pyrexia) and ECGs. Unscheduled laboratory tests performed at the time of pyrexia (5.5 to 12 hours post dose) revealed that seven subjects from MAD 150 mg cohorts had Grade 1 to 4 lymphopenia and the Principal Investigator decided to discontinue further drug administration in these seven subjects. Lymphocyte counts returned to normal levels within 24 to 48 hours in all subjects. One subject from the 150 mg MAD dose cohort decided to withdraw from the study after the fifth dose.*

Following single oral doses of RO7020531, the PK of the active metabolite RO7011785 is linear and mean  $AUC_{0-inf}$  increased in a dose proportional manner from 40 mg to 170 mg. No PK accumulation was observed following dosing QOD dosing regimen over the 2-week period. Both single and multiple doses of RO7020531 resulted in dose-dependent increases in TLR7 response marker at the dose of 100 mg or above, and the flu-like symptoms are associated with higher PD response.

